6.1 Screening Visit

- Informed consent will be obtained.
- Information about telephone contact will be obtained. A pelvic examination will be performed to determine that the cervical os is closed. Gonorrhea and Chlamydia testing may be performed at this time if it has not been done in this pregnancy and is indicated.
- A transvaginal ultrasound examination will be performed unless a complete report is available from an adequately detailed examination within 24 hours prior to enrollment.
- Approximately 1 tablespoon of blood will be drawn for a hemoglobin and blood type if record of these values is not available (hemoglobin must have been obtained within the past 6 months). A rapid hemoglobin (via the HemoCue) may also be utilized.

If it is determined that the subject is eligible for the study, she may proceed to study enrollment.

6.2. Study Day 1 Visit

This visit may or may not occur on the same day as the screening visit.

Pre-Treatment

- If Study Day 1 does not occur on the same day as screening and there has been active vaginal bleeding since screening, the transvaginal ultrasound must be repeated.
- The subject will be questioned to obtain baseline information about her demographic characteristics and her medical, coital, menstrual, pregnancy, and contraceptive history. She will be given the following questionnaires to complete at home prior to inserting misoprostol and return at her next visit: CES-D and the Perceived Stress Scale.
- Rh-immune globulin 50 µg (“MICRhoGAM”) will be administered within 72 hours of this visit if the subject is Rh-negative and has not recently received Rh-immune globulin.
- Additional blood will be drawn (20 cc) and it will be stored for analysis of proteins and hormones.
- Vital signs, weight, and height (to calculate BMI) will be measured.
- A pelvic examination and/or Gonorrhea and Chlamydia testing may be performed if indicated
- The subject will be randomly assigned to one of the two study groups: 800µg (vaginally) misoprostol (group 1) or misoprostol 800 µg (vaginally) preceded by 200 mg mifepristone po (group 2). See Method for Assigning Subjects to Treatment Groups Section 3.1

Treatment

- If the participant is randomized to group 2, she will be given 200mg of mifepristone. She will swallow the tablet prior to being discharged from the study visit.

- All subjects will be given four 200 µg misoprostol tablets to place vaginally approximately 24 hours later at home.
- The subject will be offered prescriptions for pain relievers per local standards at each site.
- The participant will be instructed to abstain from sexual intercourse until the passage of the pregnancy has been confirmed.
- The subject will receive instructions about what to expect after misoprostol administration as per standard of care.
- A diary will be distributed to collect information about bleeding, pain medication use, and symptoms. The subject will be instructed on how to properly complete the diary. The subject should bring this diary to each visit.
- A follow-up appointment will be made for Day 3.

Treatment may be delayed per subject preference. If treatment is delayed, and there has been active vaginal bleeding since the last transvaginal ultrasound, the ultrasound must be repeated prior to dispensing drug.

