5.2. Treatment Regimen

The subject will be randomized to receive 800 µg (vaginally) misoprostol alone or 800 µg of misoprostol (vaginally) preceded by 200 mg of mifepristone (orally) 24 hours prior.

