6.4 Study Day 8 Visit (or Phone Call)

This visit will occur between study day 6-12. For those who were confirmed to have passed the pregnancy or had an aspiration procedure on Study Day 3, this visit will instead be a phone call to evaluate for bleeding or possible need for further evaluation.

- If this visit occurs in person, vital signs will be measured.

- Subjects who are scheduled to return for a visit on study day 8 will have a transvaginal ultrasound examination performed by a masked ultrasonographer. A pelvic exam will be performed if indicated.
- If no gestational sac is seen, the subject will receive contraception counseling and plan for a follow-up phone call on study day 30.
- If the examination demonstrates a persistent gestational sac, the options will be given for an aspiration procedure, a second dose of misoprostol or expectant management. The expectant management plan will include weekly visits for evaluation until the miscarriage is complete. These weekly visits will include a review of symptoms and adverse events, and an exam or ultrasound as indicated. They will also be offered active management if appropriate.
- Completed diary will be reviewed with subject. Adverse events will be reviewed and recorded.
- If subject requires additional visits, a new diary will be distributed.

6.5 30 Day Phone Call

All subjects will be contacted by telephone 30 days (range 25-36) after study day 1. Information on additional symptoms and treatment during the extended period will be recorded. Subjects will be asked to report any additional adverse events. The Post-Study Acceptability Questionnaire will be completed at this time, which will include the following scales: CES-D, Perceived Stress Scale, Adverse Child Experiences Questionnaire (ACE), and the Social Support Interview. The primary outcome of success (tissue expulsion after 1 dose of misoprostol with no additional need for medical/surgical intervention) or failure is ultimately confirmed at this 30-day point.

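### CES-D and Perceived Stress scores taken before misoprostol are collected after unblinded allocation, so they are not pre-randomisation values and should not serve as a baseline as the schedule stands

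*Combined protocol and SAP*

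**What the plan says.** Section 6.2 (Study Day 1 Visit) places the questionnaires under Pre-Treatment. Their bullet opens with "The subject will be questioned to obtain baseline information about her demographic characteristics" and with her history. A separate sentence then says that she is "given the following questionnaires to complete at home prior to inserting misoprostol", and that the forms to "return at her next visit: CES-D and the Perceived Stress Scale".

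The last Pre-Treatment bullet is the allocation: "The subject will be randomly assigned to one of the two study groups". Under Treatment, a woman in group 2 receives mifepristone during the same visit: "She will swallow the tablet prior to being discharged from the study visit". Misoprostol comes later: "All subjects will be given four 200 µg misoprostol tablets to place vaginally approximately 24 hours later at home". The section also allows treatment to be delayed if the woman prefers.

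Section 5.2 gives the two regimens as "800 µg (vaginally) misoprostol alone or 800 µg of misoprostol (vaginally) preceded by 200 mg of mifepristone (orally) 24 hours prior". No placebo is described, and sections 6.3 and 6.4 mention masking only for the ultrasonographer. Section 6.5 repeats the scales by telephone at Day 30, in a questionnaire "which will include the following scales: CES-D, Perceived Stress Scale" and two further instruments.

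Section 3.3 makes quality of life a secondary endpoint. Section 7.2 lists satisfaction, anxiety and acceptability among the outcomes, but it names neither scale and does not say how the pre-misoprostol scores will be used.

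**The concern.** Two self-report scales measured once before misoprostol and again at Day 30 look like a before-and-after pair, and an analyst would naturally treat the first as baseline. A baseline must precede allocation. Here the woman answers knowing her arm, and in group 2 usually after the first study drug. Reported mood and stress could respond to either.

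If the first score is shifted by allocation, subtracting it or adjusting for it carries the shift, with reversed sign, into the Day 30 contrast. An arm difference in these scores could also be mistaken for chance imbalance or for faulty randomisation. Section 7.2 provides for adjustment when an imbalanced variable also affects outcome. Its opening balance check speaks of demographic characteristics, so extending it to these scales is a possibility and not a stated plan.

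Timing is also unverified. The forms come back at a visit that section 6.3 allows on treatment days 3 to 6. No completion date or time is requested, and the compliance checks in section 5.5 cover diaries and medication packaging only.

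**Working it through.** **Order of events, from section 6.2**

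1. Day 1, clinic: forms handed over.
2. Day 1, clinic: randomisation, with no placebo.
3. Day 1, clinic, group 2 only: mifepristone swallowed before discharge.
4. Home: forms completed, at any time before step 5.
5. Home, about 24 hours after the visit: misoprostol.
6. Next visit: forms returned.
7. Day 30, telephone: the same scales repeated.

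Step 4 follows step 2 in both arms and follows step 3 in group 2. The exception is delayed treatment: a woman could then complete the forms before mifepristone. The documents do not say whether randomisation would be delayed too.

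**What a shift would do.** The plan gives no power, effect size or analysis for these scales, so there is no figure to reproduce. This is an illustration only.

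- From section 7.1: n = 150 per arm.
- Assumed, not in the documents: complete data; no true Day 30 difference; equal SDs; pre-score in group 2 shifted by d = 0.1 to 0.3 SD; correlation of pre-score with Day 30 score ρ = 0.3 to 0.7; two-sided 5% test, normal approximation.

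Covariate adjustment: bias = −ρd; SE = √[(2/n)(1 − ρ²)].

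Change score: bias = −d; SE = √[(2/n) × 2(1 − ρ)].

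Rejection rate = 1 − Φ(1.96 − |bias|/SE) + Φ(−1.96 − |bias|/SE).

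Worked case, d = 0.2 and ρ = 0.5:

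- Adjusted: bias −0.10; SE = √(0.01333 × 0.75) = 0.100; ratio 1.00; rejection 17.0%.
- Change score: bias −0.20; SE = √(0.01333 × 1) = 0.1155; ratio 1.73; rejection 41.0%.

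| d (SD) | ρ | Adjusted: bias (SD) | Adjusted: rejection | Change: bias (SD) | Change: rejection |
|---|---|---|---|---|---|
| 0.1 | 0.3 | −0.03 | 5.9% | −0.1 | 11.3% |
| 0.1 | 0.5 | −0.05 | 7.9% | −0.1 | 13.9% |
| 0.1 | 0.7 | −0.07 | 13.6% | −0.1 | 20.1% |
| 0.2 | 0.3 | −0.06 | 8.5% | −0.2 | 31.0% |
| 0.2 | 0.5 | −0.10 | 17.0% | −0.2 | 41.0% |
| 0.2 | 0.7 | −0.14 | 39.7% | −0.2 | 60.9% |
| 0.3 | 0.3 | −0.09 | 12.9% | −0.3 | 59.3% |
| 0.3 | 0.5 | −0.15 | 32.3% | −0.3 | 73.8% |
| 0.3 | 0.7 | −0.21 | 72.1% | −0.3 | 91.8% |

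Allowing for the plan's 5% loss (150 × 0.95 = 142.5, taken as 142) changes little. The adjusted analysis then gives 6.6% at d = 0.1, ρ = 0.4 (bias 0.04, SE 0.109) and 47.4% at d = 0.3, ρ = 0.6 (bias 0.18, SE 0.095).

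With d = 0 there is no bias. An unadjusted comparison of Day 30 scores does not use the pre-score, so it is unaffected for any d.

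**The case against.** The strongest reply is that the plan never calls these scores a baseline. In section 6.2 the word attaches to the questioning about demographics and history. The questionnaire sentence sets its own timing, before misoprostol, and the schedule meets that. Section 7.2 specifies no change score, adjusted comparison or balance check for either scale. At Day 30 they sit inside an acceptability questionnaire, and section 7.2 assesses acceptability descriptively. All of this stands, and it limits the point to a conditional one.

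Three stronger readings are tempting, and the documents do not support them:

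- **That the planned Day 30 comparison is biased, or that this trial has an inflated error rate.** No planned analysis uses the pre-scores. The percentages above depend on assumed shifts and correlations and on analyses that the plan does not contain.
- **That forms will be completed after misoprostol.** The instruction says the opposite. What remains is that a late form could not be recognised, because no completion time is recorded.
- **That every group 2 woman answers after mifepristone.** Delayed treatment leaves room for exceptions.

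The reply does not remove the sequence itself. Nor does it explain what the pre-misoprostol scores are for, if not for comparison with the Day 30 repeat.

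**Conclusion.** The point holds in a limited form. As scheduled, the only CES-D and Perceived Stress scores before Day 30 are post-allocation in both arms and, unless treatment is delayed, post-mifepristone in group 2. That the woman knows her arm is inferred from the absence of a placebo and from masking being described only for the ultrasonographer.

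The consequence is confined to secondary psychological measures and to uses that the plan leaves open without specifying them. Within the assumed ranges and at 150 per arm, the false-positive rate would run from about 6% to 72% with adjustment and from 11% to 92% with change scores. These ranges show sensitivity and are not estimates for this trial. The case for acting is that the change costs little and that a pre-randomisation score cannot be recovered later.

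**What to change.** In section 6.2, have both scales completed in the clinic at the Day 1 visit, after consent and before the REDCap randomisation. In section 7.2, name these values as the covariate in the Day 30 comparison of each scale. This adds an analysis that the plan does not now contain. It also gains precision: at an assumed ρ of 0.5 the standard error falls by a factor of √(1 − 0.25) = 0.87. The cost is a few more minutes at the visit and a sentence in each section.

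If the forms must stay at home, call them post-randomisation, pre-misoprostol scores, have the woman record the date and time of completion, and compare Day 30 scores without adjusting for them. They should then not be used for change scores or to judge balance.

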6.3 Study Day 3 Visit

This visit will occur between treatment day 3-6, ideally at least 24 hours after administration of misoprostol.

- Vital signs will be measured.
- A transvaginal ultrasound examination will be performed by a masked ultrasonographer. A pelvic exam will be performed if indicated.
- If the gestational sac is absent, the subject will need no further scheduled visits. She will receive a contraceptive prescription or device, if desired. She will receive a phone call on study day 8 to assess well-being.
- If the gestational sac is still present, the participant may opt for an aspiration procedure, a second dose of misoprostol or expectant management.
- If she opts for a second dose of misoprostol or expectant management she will be scheduled for an office visit on study day 8.
- If she has an aspiration procedure, no further visits are required and her study day 8 visit will instead be a phone call. She will receive a contraceptive prescription or device, if desired. If she chooses an aspiration procedure, but does not have the procedure prior to the day 8 time point, she will come to the office for the study day 8 visit for assessment.
- Approximately 20 cc of blood will be drawn and stored for analysis of possible biomarkers.
- Completed diary will be reviewed with subject. Adverse events will be reviewed and recorded.
- If subject requires a visit on study day 8, a new diary will be distributed.

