The acceptability will be assessed by descriptive statistics. We will query participants using validated instruments [9,11,63] about perceived acceptability of the procedure, adverse effects, pain, bleeding, and duration of symptoms and treatment, as well as whether the procedure met the expectations for the experience, would be chosen again, and would be recommended to a friend. The mean values \pm standard deviation of the VAS measurements will be compared using the Student's t-test. As above, bivariate methods will also be used to assess any demographic or clinical characteristics that may be associated with acceptability. We will calculate treatment recovery time [63] as assessed by the extent to which participants missed school or work due to treatment recovery, required the help of others in their recovery, and the duration of physical and self-reported psychological symptoms as recorded on the daily diary maintained by participants.

In order to assess the impact of our results on health care costs, we will calculate whether there is an increased or decreased cost from adding mifepristone to the medical management regimen. Mifepristone is priced at \$90 per tablet. However, depending on how much it decreases extra medical and surgical care, this price may be more than off-set [64]. The cost for each woman will be computed including hospital resource costs (ER visits, physician time, ultrasounds, etc), cost to the woman (days off work, childcare expenses, travel expenses, etc), and lost productivity. Total costs will be compared between treatment arms using standard bivariate techniques. The nonparametric bootstrap method will be used to present cost-effectiveness acceptability curves and net benefit statistics at alternative willingness to pay thresholds held by decision makers for preventing a need for surgery [65].

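### A new diary goes only to women who still need a visit, so symptom duration taken from the diary is recorded over a window that depends on the Day 3 outcome and is expected to differ by arm

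*Combined protocol and SAP*

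**What the plan says.** Section 6.2 (Study Day 1 Visit) applies to all women: "A diary will be distributed to collect information about bleeding, pain medication use, and symptoms". They are to bring the diary to each visit.

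Section 6.3 (Study Day 3 Visit) has the completed diary reviewed with the subject. On timing: "This visit will occur between treatment day 3-6, ideally at least 24 hours after administration of misoprostol". What follows depends on the ultrasound and on the woman's choice:

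- Sac absent: "If the gestational sac is absent, the subject will need no further scheduled visits". She is telephoned on Day 8.
- Sac present, aspiration done: "If she has an aspiration procedure, no further visits are required and her study day 8 visit will instead be a phone call".
- Sac present, second dose or waiting: "If she opts for a second dose of misoprostol or expectant management she will be scheduled for an office visit on study day 8". A woman who chooses aspiration but has not had it by Day 8 also comes to the office.

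The diary rule follows that split: "If subject requires a visit on study day 8, a new diary will be distributed". Section 6.4 repeats it one step later: "If subject requires additional visits, a new diary will be distributed".

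Section 7.2 says treatment recovery time will be calculated from missed school or work, help needed from others, and the "duration of physical and self-reported psychological symptoms as recorded on the daily diary maintained by participants". For continuous outcomes in general, the same section names a t-test, or a rank-sum test or log transformation. It gives no common diary period and no rule for a symptom still present on the last diary day.

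**The concern.** Duration read from a diary cannot exceed the length of the diary. Here the length is set after randomisation by whether the sac has gone at Day 3 and, if not, by the rescue chosen. The primary hypothesis is that the arms differ on the first of these. The arm with more successes therefore has more women whose record ends at the Day 3 visit, and its recorded durations are cut shorter for that reason alone.

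The cut can come early. Misoprostol is placed about 24 hours after the Day 1 visit, so a woman seen on Day 3 may have only about one diary day after misoprostol. The Day 8 call to resolved women asks about bleeding, so the protocol itself allows for bleeding after that point. At stake is whether a shorter recorded recovery in the combination arm could be read as a treatment benefit.

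**Working it through.** **Inputs.** From Section 7.1: success of 85% with the combination (C) and 70% with misoprostol alone (M), and 150 women per group. From Sections 6.3 and 6.4: Day 3 visit on treatment day 3-6, Day 8 visit on study day 6-12. Assumed, because the documents do not give them: the share *q* of failures aspirated at Day 3 (0 to 1, the same in both arms), the true symptom durations, and primary failure taken as sac present at Day 3.

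**The plan's own figure.** The documents give no figure for diary duration. The sample size confirms the design rates: for 70% versus 85%, two-sided 5%, 80% power (assumed) and continuity correction, n = 134 per group, as stated in Section 7.1. Without the correction it is 121.

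**Share given a second diary** = (1 − success) × (1 − q).

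**Mean diary window** = 3 + 5 × that share, for nominal diaries ending on Day 3 or Day 8.

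| q | Second diary, M | Second diary, C | Mean window, M | Mean window, C | Difference |
|---|---|---|---|---|---|
| 0 | 30% | 15% | 4.50 d | 3.75 d | 0.75 d |
| 0.5 | 15% | 7.5% | 3.75 d | 3.38 d | 0.38 d |
| 1 | 0% | 0% | 3.00 d | 3.00 d | 0 |

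At the late ends of the visit windows (Day 6 and Day 12) the extra window is 6 days, and the differences are 6 × 0.15 = 0.90 and 6 × 0.075 = 0.45 day. With equal success and equal choice of aspiration, the windows do not differ by arm.

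**Ceiling on the test statistic.** If every woman's symptoms outlast Day 8, recorded duration equals the window, and its variance is 25 × share × (1 − share).

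- q = 0: SE = √[25 × (0.30 × 0.70 + 0.15 × 0.85) / 150] = 0.237, so z = 0.75 / 0.237 = 3.16.
- q = 0.5: SE = √[25 × (0.15 × 0.85 + 0.075 × 0.925) / 150] = 0.181, so z = 0.375 / 0.181 = 2.07.

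**With varying true durations.** Let T be the true duration, with the same distribution in both arms and unrelated to outcome, recorded as min(T, 3) or min(T, 8). The spurious difference is then 0.15 × (1 − q) × {E[min(T, 8)] − E[min(T, 3)]}, which cannot exceed 0.15 × 5 = 0.75 day. A simulation with gamma durations (shape 4), 150 per arm and 3,000 trials per setting gave:

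| Assumed mean T | q = 0: difference; t-test rejects | q = 0.5: difference; t-test rejects |
|---|---|---|
| 4 d | 0.19 d; 30% | 0.09 d; 15% |
| 7 d | 0.46 d; 72% | 0.23 d; 40% |
| 10 d | 0.60 d; 82% | 0.30 d; 48% |
| 14 d | 0.68 d; 86% | 0.34 d; 52% |

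The nominal rejection rate is 5%.

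**The case against.** Several objections have force.

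- **Stopping is inferred.** Section 6.3 says the diary is reviewed, not collected, and the form is not in the documents. Section 6.4 is headed for a visit or a phone call, and its diary-review item is not limited to women seen in person. This stands as far as it goes. But a completed diary at Day 3, no replacement, and no return route make stopping the natural reading. If continued recording is intended, the text should say so.
- **No arm comparison of recovery time is stated.** Section 7.2 says it will be calculated, in a passage that opens with descriptive statistics, and Section 3.3 does not list it as an endpoint. This is correct. The comparison comes only from the general methods in Section 7.2. A descriptive table by arm would carry the same distortion.
- **Other sources exist.** The Day 8 call asks about bleeding. The Day 30 call records additional symptoms, treatment and adverse events, and includes the acceptability questionnaire. Section 7.2 says participants will also be asked about the duration of symptoms, and missed work and help needed may come from there. This stands, and it limits the point to duration taken from the diary. These contacts rely on recall, and Section 7.2 names the diary for duration.
- **Some of the extra symptom time is real.** Symptoms after a second dose are a consequence of failed treatment in a pragmatic trial. That is so, but it does not justify leaving the same days unrecorded in the other women.
- **Failure is not the same as sac present at Day 3.** Section 7.2 also counts intervention within 30 days, so some failures would have no second diary. The shares above are approximate for that reason.

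**Conclusion.** The point holds for diary-derived symptom duration, and only for that. Followed as written, the plan makes the recorded window depend on the Day 3 outcome and the rescue chosen, and the design expects the first to differ by arm. The direction favours the arm with more Day 3 successes, provided that some failures continue to a Day 8 visit.

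For nominal diaries of 3 or 8 days, 0.75 day is an upper bound. About 0.1 to 0.7 day is a plausible range under the assumed durations with up to half of failures aspirated, and the effect falls to zero as the aspirated share approaches 100%. The z-values of 3.16 and 2.07 are ceilings, because they let every woman's symptoms outlast Day 8 and ignore variation in true duration. The true durations and the aspiration share are assumptions.

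A reader might infer that the side-effect endpoint is biased towards the combination by construction. The documents do not support this. Section 8.1 draws symptoms from self-report and medical records as well as diaries, and the calls and questionnaire reach all women. Side-effect frequency is affected only as far as it relies on diary days. Nor does the point touch the primary endpoint or the sample size.

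**What to change.** Give every participant at Day 1 the same diary for the same fixed number of days, through the Day 8 contact and regardless of the Day 3 finding or any procedure. State the day from which days are counted, since Section 6.3 uses treatment days, Section 6.4 uses study days, and treatment may be delayed. Women with no Day 8 visit can read the diary out at the call already planned or mail it back. In Section 7.2, define diary-derived duration over that common period, compare arms only within it, and name the source for any later duration.

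If this is not feasible, there are two fallbacks. One is to restrict the diary comparison to a fixed number of days observed in all women, for example through Day 3; all days before the Day 3 visit would not do, because that visit ranges over days 3 to 6. The other is to treat duration as censored at the last diary day. This is weaker, because the censoring time is itself tied to the Day 3 outcome.

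The cost is a longer diary, a slightly longer Day 8 call and some unreturned diaries. It needs no extra visit and no change to the sample size.
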